6.1 Information to be collected on screening failures

All subjects who have signed informed consent but not randomized will have the disposition, demographics, inclusion/exclusion, informed consent, rescreening, withdrawal of consent (if subject withdrew consent) and serious adverse event (SAE) data collected. Adverse events that are not SAEs will be followed by the investigator or primary care physician and collected only in the source data.

All patients who have signed informed consent and have received high dose ICS/LABA medication, but discontinue prior to randomization (run-in failures) should have all data for the visits they attended and the summary pages (Adverse Event, Concomitant Medication, Dosage Administrative Record) completed. All adverse events occurring after informed consent is signed should be recorded on the Adverse Event CRF.

Investigators will have the discretion to record abnormal test findings on the medical history CRF whenever in their judgment, the test abnormality occurred prior to the informed consent signature.

6.2 Patient demographics/other baseline characteristics

Patient demographic and baseline characteristic data to be collected on all patients include:

- Age (calculated)
- Sex
- Race and ethnicity
- Patients initials (where allowed by local legislation)
- Height and Weight
- BMI (calculated)
- Baseline physical examination (not databases other than in the context of relevant medical history)
- Vital signs
- ECG
- Date of diagnosis of asthma
- Relevant medical history/ current medical condition present before signing the informed consent
- Smoking history and status
- Asthma Quality of Life (AQLQ+12)
- Asthma Control (ACQ-5)
- Blood eosinophil counts at Run-in Visit
- Prior concomitant medication (Both asthma related and non-asthma related)
- Pre and post-bronchodilator spirometry (run-in spirometry and reversibility testing)

6.3 Treatment exposure and compliance

Study drug compliance will be assessed by the investigator and/or study personnel at designated visits by recording tablet counts from the previously dispensed bottles. This information must be captured in the source document at each visit. All study drug dispensed and returned must be recorded in the Drug Accountability Log. Where necessary, the Investigator will discuss compliance issues with the patient.

Start and end dates of only missed doses of study drug administered since the last dispensing visit will be recorded in the eCRFs (study drug dosage administration record summary page) at visits specified in the table of assessments (Table 6-1).

All doses of study drug taken at the clinic visits must be from the newly assigned medication bottles, **except at EOT Visit when the medication returned by the patient should be used.**

6.4 Efficacy

The following assessments of efficacy will be performed:

- Systemic Corticosteroids use
- Health Status (PROs: AQLQ+12, ACQ-5)
- Biologic therapy administered during the treatment period

6.4.1 Systemic corticosteroids use

All patients will be provided with Oral Corticosteroids that can be used according to the asthma plan.

The total amount of daily OCS (number of tablets taken in the previous 12 hours) will be recorded morning and evening by the patient, in the eDiary/PEF

Investigators should instruct patients to record any OCS intake during the treatment period, on the eDiary/PEF device. At each study visit investigators and/or study personnel will count the number of OCS capsules taken (as part of the drug accountability), review OCS intake recorded on the eDiary by the patient, interview the patient on doses taken and enter it on the eCRF along with the start date, end date and the reason for the OCS intake.

Patients will be asked to return all unused non-study treatments and packaging at the end of the study or at the time of discontinuation from the study.

During certain circumstances (e.g. Hospitalization) patients might be taken injectable corticosteroids. This data will also be collected on the eCRF.

6.4.2 Health status (Patient Reported Outcomes)

A patient-reported outcome (PRO) is any report of the status of a patient's health condition that comes directly from the patient, without interpretation of the patient's response by a clinician or anyone else. Patient-reported outcomes may provide quantitative information for patients regarding the 'impact on daily life', which is of key importance, for patients and their physicians and also for health technology assessments. In this study, two PROs are used to assess the impact of uncontrolled asthma and the disease's management: Asthma Quality of Life Questionnaire (AQLQ+12) and the shortened version of Asthma Control Questionnaire (ACQ-5). All PROs

should always be completed before any other assessments are performed to avoid influencing the responses. When occurring at the same visit they are to be completed in the following order: AQLQ+12 and ACQ-5.

6.4.2.1 Asthma Quality of Life Questionnaire (AQLQ+12)

The AQLQ+12 is a 32-item disease specific questionnaire designed to measure functional impairments that are most important to patients with asthma (the questionnaire is included in [Section 19](#)). It consists of 4 domains symptoms, emotions, exposure to environmental stimuli and activity limitation. Patients are asked to recall their experiences during the previous 2 weeks and to score each item on a 7-point scale ([Juniper et al 1992](#), [Juniper et al 1993](#), [Juniper et al 2005b](#)). The overall AQLQ score is the mean response to all 32 questions. Clinically important differences in scores between any two assessments have been determined by the authors of the AQLQ. Changes in scores of 0.5 to 1.0 are considered clinically meaningful; 1.0 to 1.5 as moderate and > 1.5 as marked clinically important differences for any individual domain or for the overall summary score ([Juniper et al 1994](#)).

The AQLQ should be completed by the patient at the investigator's site as per the Assessment Schedule table (see [Section 6](#)).

6.4.2.2 Asthma Control Questionnaire (ACQ-5)

In this study, the ACQ-5 will be used to assess improvements in asthma symptom control. The original ACQ consists of 7 items: 5 items on symptom assessment, 1 item on rescue bronchodilator use, and 1 item on airway calibre (% FEV1 predicted). As the Spirometry assessments are performed centrally, the rescue bronchodilator use and % FEV1 predicted are not included in the version of ACQ chosen for this study.

The ACQ-5 will be self-administered at the clinic and it only takes a few minutes to complete. Patients will be asked to recall how their asthma has been during the previous week and to respond to the symptom questions on a 7-point scale (0=no impairment, 6=maximum impairment). The questions are equally weighted and the ACQ-5 score is the mean of the 5 questions and therefore between 0 (totally controlled) and 6 (severely uncontrolled) ([Juniper et al 1999](#); [Juniper et al 2005a](#)).

The ACQ-5 should be completed by the patient at the investigator's site as per the Assessment Schedule table (see [Section 6](#)).

6.4.3 eDiary

All patients will be provided with a patient electronic diary (referred to as eDiary/ePEF) to record daily asthma symptoms, peak flow, rescue medication (salbutamol/albuterol) and OCS use. Patients will be instructed to routinely complete the patient diary twice daily – at the same time each morning and each evening, approximately 12 hours apart. The eDiary/ePEF recordings are to be reviewed at the clinic visits as detailed in [Table 6-1](#) until study completion. Sites and patients will receive appropriate training and guidance on the use of the eDiary device.

The study will use the asthma diary ([Santanello et al 1997](#)). The information detailed below will be collected in the eDiary/ePEF. Daytime asthma symptoms will be rated on a 0 to 6 scale and nocturnal asthma symptoms will be rated on a 0 to 3 scale

6.4.3.1 Daily Symptom Scores

The asthma diary contains daytime and nocturnal asthma symptom questions as delineated below. The format of the electronically administered asthma diary may vary.

Symptom diary scale questions

Table 6-2 Daytime symptom diary scale questions

1) How often did you experience asthma symptoms today?						
0	1	2	3	4	5	6
None of the time						All of the time
2) How much did your asthma symptoms bother you today?						
0	1	2	3	4	5	6
Not at all bothered						Severely bothered
3) How much activity could you do today?						
0	1	2	3	4	5	6
More than usual activity						Less than usual activity
4) How often did your asthma affect your activities today?						
0	1	2	3	4	5	6
None of the time						All of the time

Table 6-3 Nocturnal diary scale question

1) Did you wake up with asthma symptoms?			
This can be awakening in the middle of the night or on awakening in the morning			
No	Once	More than once	Awake "all night"

6.4.3.2 Number of inhalations of Rescue Medication

The total number of inhalations used of rescue medication (number of puffs taken in the previous 12 hours) will be recorded morning and evening by the patient, in the eDiary/ePEF.

6.4.3.3 Peak expiratory flow (PEF)

PEF will be measured at consistent times for a patient, in the morning and evening each day during the study from Run-In to study completion. The measurements will be performed, using an eDiary/ePEF provided to the patients.

Patients should be encouraged to perform morning and evening PEF measurements BEFORE the use of any rescue medication, and patients will be asked to record if they have taken their SABA medication 6 hours prior to the peak flow assessment.

At each time point, the patient will be instructed to perform 3 consecutive maneuvers within approximately 10 minutes. These PEF values are captured in the eDiary /ePEF

6.4.4 Worsening of asthma (and related eDiary alerts)

Asthma worsening criteria will be programmed into the eDiary/ePEF apart from criterion 4 below.

The data captured in the eDiary/ePEF will be used to alert the patient and/or investigator to possible signs of worsening asthma.

The investigator should instruct the patient to contact the investigator if the patient develops one or more of the following asthma worsening criteria at any time during the trial from the run-in onwards. Patients may also receive an alert via their eDiary requesting them to contact their investigator:

1. An increase in SABA use on at least 2 of any 3 consecutive days exceeding the equivalent of 8 puffs/day (diary alert) *;
2. Nighttime awakenings requiring SABA use on at least 2 out of any 3 consecutive nights (diary alert)*;
3. <60% of PEF compared to baseline (diary alert)*; or
4. Urgent unscheduled clinic visit due to asthma-related deterioration.

*Note: The baseline for the run-in period is set the start of Run-in. The baseline during the treatment is set at the beginning of treatment (Day 1).

If patients develop any of the above criteria, the patient should notify the investigator and be evaluated by the investigator and treated as clinically appropriate. If any of these criteria are met while a patient is in the treatment or run-in periods of the study, they may be withdrawn if, in the opinion of the investigator, it is appropriate to do so.

Worsening of asthma symptoms may require unscheduled evaluation between visits. Study site personnel must be available to monitor and document the patient's progress until the asthma worsening has resolved.

6.4.5 Biologic therapy administered during the treatment period

As part of the flexible therapy, investigators are allowed to prescribe biologics from randomization visit onwards.

Given the delay to get access to the treatment in some countries, the date of prescription by the investigator should be recorded in addition to the start date and end date of the treatment. The dose, unit and reason for the treatment will also be collected.

6.4.6 Appropriateness of efficacy assessments

The measures described above are standard outcome measures in asthma studies.

6.5 Safety

The following safety assessments will be performed:

- Medical history and physical examination
- Adverse events including serious adverse events
- Asthma Exacerbations

- Height and weight
- ECG
- Laboratory evaluations (Hematology, Blood chemistry including HbA1c, Urinalysis)
- Pregnancy (female patients); additional pregnancy testing might be performed if requested by local requirements
- Serious asthma outcomes (asthma-related hospitalizations, intubations or deaths)

Spirometry will also be used to monitor the safety of patients during the study. Patients will be provided with an eDiary/ePEF. The data captured in the eDiary/ePEF will be used to alert the patient and/or investigator to possible signs of worsening of asthma.

A central laboratory will be used to analyze and report blood chemistry/hematology/urinalysis and urine chemistries.

A central ECG vendor will be used to collect, assess and report ECGs.

6.5.1 Medical history and physical examination

A complete physical examination will be performed at Screening Visits and EOT visit, or TD (if a patient discontinues investigational treatment but continues with study participation). It will include the examination of general appearance, skin, neck (including thyroid), eyes, ears, nose, throat, lungs, heart, abdomen, back, lymph nodes, extremities, vascular and neurological. If indicated based on medical history and/or symptoms, rectal, external genitalia, breast, and pelvic exams will be performed.

Information for all physical examinations must be included in the source documentation at the study site. Significant findings that are present prior to informed consent being granted must be included in the Relevant Medical History/Current Medical Conditions screen on the patient's eCRF. Significant findings made after informed consent is given which meet the definition of an Adverse Event must be recorded on the Adverse Event screen of the patient's eCRF.

6.5.2 Asthma Exacerbations

The following definitions of exacerbations are used in this study.

A **mild asthma exacerbation** is defined as one or more of the following:

- Increase of asthma symptoms
- An increase in SABA use on at least 2 of any 3 consecutive days exceeding the equivalent of 8 puffs/day (diary alert)
- Nighttime awakenings requiring SABA use on at least 2 out of any 3 consecutive nights (diary alert)
- <60% of PEF compared to baseline (diary alert)

A **moderate asthma exacerbation** is defined as treatment with 'rescue' systemic corticosteroids for greater than or equal to 3 days either as an outpatient or in emergency department visits (Emergency department visit less than or equal to 24 hours).

A **severe asthma exacerbation** is defined as:

- Treatment with ‘rescue’ systemic corticosteroids for greater than or equal to 3 days and hospitalization; or
- Treatment with ‘rescue’ systemic corticosteroids for greater than or equal to 3 days and emergency department visit (greater than 24 hours*); or
- Death due to asthma

*An emergency room visit greater than 24 hours is considered to be a hospitalization.

‘Rescue’ systemic corticosteroids are tablets, suspension, or injection, or an increase of a patient’s maintenance systemic corticosteroids of ≥ 2 fold (i.e., at least doubling of the maintenance dose of systemic corticosteroids). A single depo-injectable dose of corticosteroid will be considered the equivalent to a 3-day course of systemic steroids (Reddel et al 2009). Endotracheal intubations will be captured on the CRF.

Scheduled spirometry should not be performed during an exacerbation until it has completely resolved.

If patients experience an asthma attack/exacerbation requiring systemic corticosteroids, hospitalization, or emergency room visit during the screening period, they may be re-screened once with the re-screening of the patient occurring 6 weeks or more after recovery from the asthma exacerbation.

In case of an asthma exacerbation, the patient should be encouraged by the site to contact it for advice. If necessary, an unscheduled visit to the site may be arranged.

6.5.3 Vital signs

Vital signs will be performed at site visits specified in the table of assessments (Table 6-1). Measurements will include systolic and diastolic blood pressure, pulse rate, and body temperature.

6.5.4 Height and weight

Height in centimeters (cm) will be measured at the visits specified in the table of assessments (See Table 6-1).

Body weight (to the nearest 0.1 kilogram [kg] in indoor clothing, but without shoes) will be measured at the visits specified in the table of assessments (See Table 6-1).

Body Mass Index (BMI) will be calculated as the weight in kg divided by the height in meters squared.

6.5.5 Laboratory evaluations

A central laboratory will be used for analysis of all specimens detailed in this section. Details on the collections, shipment of samples and reporting of results by the central laboratory are provided to investigators in the laboratory manual.

Details on clinically notable laboratory findings are defined in Section 13.

6.5.5.1 Hematology

Hemoglobin, hematocrit, red blood cell count, white blood cell count with differential, and platelet count will be measured according to the assessment schedule in [Table 6-1](#). Other reflex testing will be performed as outlined in the laboratory manual.

6.5.5.2 Clinical chemistry

BUN/urea, creatinine, creatine kinase, total bilirubin, AST, ALT, alkaline phosphatase, gamma-glutamyl transpeptidase, lactate dehydrogenase, sodium, potassium, chloride, calcium, magnesium, iron, bicarbonate, cholesterol, triglycerides, high-sensitivity C-reactive protein, phosphorus, total protein, albumin, glucose, uric acid, amylase, lipase, CK-MB and Troponin-I (in response to CK results outside of the normal range), HbA1c (collected at start of Run-in Visit and EOT only) and immunoglobulins (total and specific IgE, as specified in the laboratory manual), will be measured according to the assessment schedule in [Table 6-1](#). Other reflex testing will be performed as outlined in the laboratory manual.

If the total bilirubin concentration is increased 1.5 times and above the upper limit of normal range, the total bilirubin will be differentiated into the direct and indirect reacting bilirubin.

All patients with laboratory tests containing clinically significant abnormalities should be followed until the values return to within the normal ranges or until a clinical explanation is identified, even after study medication has discontinued.

6.5.5.3 Urinalysis

Urine for urinalysis and urine chemistry will be collected according to the collection schedule in [Table 6-1](#). All samples for urinalysis and urine chemistry will be sent to the central laboratory for analysis. The urinalysis evaluation by the central laboratory will include a urine dipstick for specific gravity, protein, glucose, leukocytes and blood and, if required, a microscopic examination. Urine chemistry and microscopic examination of the urine will be performed by the central laboratory as delineated in [Section 15](#) “Specific Renal Alert Criteria and Actions” and in [Section 7.4](#) “Renal Safety Monitoring” of this protocol. Other reflex testing will be performed as outlined in the laboratory manual.

6.5.6 Electrocardiogram (ECG)

ECGs will be measured according to the assessment schedule in [Table 6-1](#). At Screening Visit, an ECG will be measured to test for eligibility for trial inclusion.

ECGs must be recorded according to the ECG investigator manual in the supine position to ensure a stable baseline. The preferred sequence of cardiovascular data collection during study visits is PRO collection first, followed by ECG, and then other study procedures. The Fridericia QT correction formula (QTcF) must be used for clinical decisions.

Single 12 lead ECGs are to be collected with ECG machines supplied by the core laboratory. Full details of all procedures relating to the ECG collection and reporting will be contained in an investigator manual to be provided to each investigator site.

The original trace will be sent electronically for central review directly from the ECG machine. Two ‘identical’ duplicate print-outs will be generated and kept at the investigator site as source

documentation and as back-up for submission to the central laboratory in case of problems with the electronic transmission. Each page of the ECG tracing must be labeled with study number (CQAW039A2323), subject initials (where this is allowed according to local regulations), subject number, date and time, and filed in the study site source documents.

For any ECGs with subject safety concerns, two additional ECGs must be performed to confirm the safety finding and copies forwarded to the central ECG laboratory for assessment. Clinically significant ECG findings prior to dosing with study drug must be discussed with the Novartis responsible person or designee.

Clinically significant abnormalities must be recorded on the relevant section of the medical history/Current medical conditions/AE CRF / e(CRF) page as appropriate.

In the event that the central cardiologist reports that an ECG is abnormal, then the investigator must comment as to whether the ECG abnormality is either clinically significant or clinically insignificant. If necessary a cardiologist may be consulted.

6.5.7 Pregnancy

All women of child bearing potential will have a serum pregnancy test at start of Run-In Visit and a urine pregnancy test at all site visits. No pregnancy testing will be performed when the visit is performed as a telephone call.

Pregnancy testing will begin at the visit a patient is first identified as being of child bearing potential.

In countries where monthly pregnancy testing is required for women of child-bearing potential by local laws or regulations, these patients will perform home urine pregnancy testing on the day of all telephone visits. These female patients will report the results of their home urine pregnancy test as “positive” or “negative” to study site staff as part of the telephone visit and the results will be recorded in source documents.

A positive urine pregnancy test requires immediate interruption of study medication until serum β -hCG is performed and found to be negative. If positive, the patient must be discontinued from the study treatment.

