- Modify in-clinic study visit frequencies to 8 weeks intervals after week 12, interspaced with telephone contacts.
- Add additional collection of hematology, clinical chemistry and urinalysis in all in-clinic visits

In addition, clarifications has been included as well

- correct abbreviations on the summary section
- clarifications on treatment of patients after study end
- misspells

Changes to the protocol

Updated visit schedule sequence between telephone contact (TC) and in-clinic visits. In-clinic visits (week 6, 12, 20, 28, 36, 44, 52) TC visits (week 16, 24, 32, 40, 48, 54)

Added additional hematology, clinical chemistry and urinalysis at all in-clinic visits on the visit schedule and assessments section 6

Corrected abbreviations in the summary section on the primary analysis portion.

Clarifications added on sections 5.5.6, 5.6.1 and table 6.1.

[figure not shown]
Protocol summary

Protocol number	CQAW039A2323
Full Title	A 52-week, multicenter, randomized, double-blind, double-dummy, parallel-group, placebo-controlled study of fevipiprant once daily plus standard-of-care (SoC) for reduction of systemic corticosteroids (oral and parenteral) use in patients with severe asthma
Brief title	SCS avoidance study in severe Asthma Patients
Sponsor and Clinical Phase	Novartis 3b
Investigation type	Drug
Study type	Interventional
Purpose and rationale	
There is a correlation between Systemic Corticosteroids (SCS) use and Adverse Events (AEs). Sustained use of SCS is associated with significant side effects, including growth retardation in children, as well as osteoporosis, diabetes, cardiovascular adverse events, muscular weakness, skin atrophy and cataract. This translates in an advantage for AE avoidance for those patients that do not use any SCS. Alternative asthma therapies that reduce the need for SCS are urgently needed, especially if given orally, such as fevipiprant.
 
The overall purpose of this study is to determine the efficacy of fevipiprant (150 mg and 450 mg once daily), compared with placebo, as add-on to GINA 2018 treatment step 4 or 5 standard-of-care (SoC) asthma therapy, in terms of avoidance of SCS use over 52 weeks. This will be measured in patients with inadequately controlled severe asthma (Asthma Control Questionnaire score (ACQ-5) ≥ 1.5) and high eosinophil counts (eosinophil count at Screening Visit ≥ 250 cells/μl), and in the overall patient population regardless of eosinophil counts.

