Weeks	-6 to -4	-4 to -1	1	1	6	12	16	20	24	28	32	36	40	44	48	52	54
Telephone Contact							TC		TC		TC		TC		TC		TC
Informed consent	X																
Inclusion / Exclusion criteria	X	X	X														
Demography	X																
Physical Examination	S															S	
Medical history/current medical conditions ⁴	X	X	X														
Asthma exacerbation history	X																
Surgeries and procedures		X	X		X	X	X	X	X	X	X	X	X	X	X	X	X
Smoking history	X																
Prior medications	X																
Concomitant medications		X	X	X	X	X	X	X	X	X	X	X	X	X	X	X	X
Safety Follow up Call																	S
Vital Signs	X	X	X		X	X		X		X		X		X		X	
Body Height	X																
Body Weight	X		X														X
Electrocardiogram (ECG)	X																X
Hematology		X		X	X	X		X		X		X		X		X	
Blood sample for serum IgE level		X															
HbA1C		X															X
Clinical Chemistry		X		X	X	X		X		X		X		X		X	
Pregnancy Test (serum)		X															
Urinalysis	X			X	X	X		X		X		X		X		X	
Pregnancy Test (Urine)			S		S	S		S		S		S		S		S	

Period	Screening			Treatment													Post-Treatment Follow Up
	Visit Name	Screening	Run-In ^{1,2}	Treatment ³												EOT or TD	
Days	-42 to -28	-28 to -1	1	1	42	84	112	140	168	196	224	252	280	308	336	364	378
Weeks	-6 to -4	-4 to -1	1	1	6	12	16	20	24	28	32	36	40	44	48	52	54
Contact IRT (IVRS/IWRS)	S	S	S	S	S	S	S	S	S	S	S	S	S	S	S	S	S
Randomization				S													
Drug dispensation				S		S		S		S		S		S			
Check IMP compliance					S	S	S	S	S	S	S	S	S	S	S	S	
Study drug administration				Daily													
Rescue medication dispense ⁵		S		As Needed													
Rescue medication review		S	S	S	S	S	S	S	S	S	S	S	S	S	S	S	
Spirometry with Reversibility Test ⁶	X	X															
Spirometry				X					X							X	
Asthma exacerbation ⁷		X	X		X	X	X	X	X	X	X	X	X	X	X	X	X
Adverse Events	X	X	X		X	X	X	X	X	X	X	X	X	X	X	X	X
Serious Adverse Events	X	X	X		X	X	X	X	X	X	X	X	X	X	X	X	X
Asthma Quality of Life Questionnaire		X	X		X	X		X		X		X		X		X	
Asthma control questionnaire (ACQ-5)	X		X		X	X		X		X		X		X		X	
eDiary Handout	S																
eDiary training	S	S	S														
eDiary/ePEF ⁸		X	X		X	X	X	X	X	X	X	X	X	X	X	X	
Check eDiary Compliance		S	S		S	S	S	S	S	S	S	S	S	S	S	S	
Study completion information																X	

Period	Screening			Treatment												Post-Treatment Follow Up	
Visit Name	Screening	Run-In ^{1,2}		Treatment ³											EOT or TD		
Days	-42 to -28	-28 to -1	1	1	42	84	112	140	168	196	224	252	280	308	336	364	378

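### Where local law requires monthly pregnancy testing, tying home tests to telephone visits leaves two six-week gaps in the first 12 weeks on drug

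*Protocol*

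**What the plan says.** Protocol Section 6.5.7 sets the general rule for women of child-bearing potential: a serum test when run-in starts, then a urine test whenever they attend the site. It then excludes remote visits: "No pregnancy testing will be performed when the visit is performed as a telephone call". One exception follows, for countries with a monthly testing requirement: "by local laws or regulations, these patients will perform home urine pregnancy testing on the day of all telephone visits". Those women report the result by telephone and the site records it in source documents. A positive urine test means stopping study medication at once until a serum test is negative.

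The visit days come from Table 6-1, and the list of changes under Amendment 1 gives the same weeks: "In-clinic visits (week 6, 12, 20, 28, 36, 44, 52) TC visits (week 16, 24, 32, 40, 48, 54"). The table row "Pregnancy Test (Urine") is marked at Day 1 and at each in-clinic visit after it, and at no telephone visit.

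Section 6.5, in its list of safety assessments, adds that "additional pregnancy testing might be performed if requested by local requirements". It gives no time points.

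**The concern.** The exception in Section 6.5.7 has one evident purpose, stated in its opening condition: "In countries where monthly pregnancy testing is required for women of child-bearing potential by local laws or regulations". It can achieve that only if site visits and telephone visits together are never more than a month apart. Amendment 1 placed telephone contacts between clinic visits only after Week 12, so before then the exception adds no test at all.

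At stake is how soon a pregnancy is detected under exposure to an investigational drug. Section 10.2 describes possible unknown risks to the fetus, and Section 5.6.2 makes pregnancy a mandatory reason to stop study treatment. When a pregnancy is found by scheduled testing, those safeguards start only once the test is done. A site that follows Section 6.5.7 to the letter would also fall short of the legal requirement that the section is meant to satisfy.

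**Working it through.** The plan states no figure of its own to reproduce; the check is a merge of two sets of visit days.

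**Inputs**

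- Urine-test days at site visits (Table 6-1, urine pregnancy row read against the Days row): 1, 42, 84, 140, 196, 252, 308, 364.
- Telephone-visit days (Table 6-1, telephone contact row; the same weeks are listed under Amendment 1): 112, 168, 224, 280, 336, 378.
- Length of a month: 30 to 31 calendar days. The SAP, Section 2.1.1, uses 365.25/12 = 30.4375 days. That is an analysis convention, used here only as a yardstick.

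**Step 1: site visits alone.** Interval = next test day − previous test day.

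- 42 − 1 = 41
- 84 − 42 = 42
- every later interval: 56 (for example 140 − 84)

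**Step 2: site visits plus home tests on telephone days.**

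| From day | To day | Interval (days) | Relative to 30.4375 |
|---|---|---|---|
| 1 | 42 | 41 | +10.6 |
| 42 | 84 | 42 | +11.6 |
| 84 | 112 | 28 | −2.4 |
| 112 to 364, each step | | 28 (nine intervals) | −2.4 |
| 364 | 378 | 14 | −16.4 |

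This makes 13 intervals: 41, 42, ten of 28, and 14. Two of the 13 exceed a month, and they are the first two on drug.

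**Step 3: what the home-test rule changes.** After Week 12 it halves the interval from 56 to 28 days, which meets a monthly requirement. Before Week 12 it changes nothing: the intervals are 41 and 42 days with or without it.

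**Step 4: possible extra delay.** Against a month of 31 days the shorter gap is 41 − 31 = 10 days too long. Against a month of 30 days the longer gap is 42 − 30 = 12 days too long. The worst-case extra delay in detection is therefore about 10 to 12 days.

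**Step 5: an illustrative correction.** Adding home tests at Weeks 4 and 8 (Days 28 and 56) gives:

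- 28 − 1 = 27
- 42 − 28 = 14
- 56 − 42 = 14
- 84 − 56 = 28

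No interval over the 52 weeks then exceeds 28 days.

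**The case against.** The strongest reply is that nothing in the protocol stops a site from testing monthly. Section 6.5.7 names days on which home tests must be done; it does not say that they may be done on no others. Section 6.5 allows extra tests where local requirements call for them, Section 11 allows further safety assessments case by case, and Section 10.1 obliges the study to follow local regulations. On that reading the text is unclear but does not force a breach. This stands in part: a careful site can close the gap without deviating. But none of these clauses gives a time point. Section 6.5.7 is the specific rule that schedules the tests, so a predictable legal requirement should not depend on each site noticing that the rule falls short.

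A second reply is that the reach is unknown. The documents do not list the participating countries, say whether any has a monthly requirement, or say how such a requirement counts a month and from what date. This stands, and it limits how much weight the point can carry.

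A third reply is that the consequence is modest. There is a serum test at run-in and a urine test on Day 1, contraception is required during dosing, and elsewhere the design accepts eight-weekly clinic testing. The delay is a worst case confined to two intervals. This too is fair as to size. It does not answer the point, which is conformity with a stricter local rule that the protocol set out to meet.

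**Conclusion.** The concern holds. The one rule in the protocol written to deliver locally required monthly testing does so only from Week 12. Before that it leaves consecutive gaps of 41 and 42 days, each longer than a month by about 10 to 12 days, during the first 12 weeks on drug.

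The conclusion assumes that at least one participating country has such a requirement, that it applies from first dose, and that monthly means no more than 30 to 31 days between tests. The practical effect is modest: it is confined to women of child-bearing potential in those countries, whose number the documents do not give, and Section 6.5 allows sites to add tests. No efficacy analysis, sample size or error rate is involved. Because SAP Section 4 records that the sponsor ended the study early, the correction now matters for the protocol as written and for any study that reuses this schedule.

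**What to change.** In Section 6.5.7, replace the link to telephone-visit days for these countries with home urine tests at the locally required interval, counted from Day 1 and continuing through treatment, with site-visit tests counting towards that interval. Add a footnote to the urine pregnancy test row of Table 6-1 that points to this rule. Home tests near Weeks 4 and 8 would be one simple way to cover the period before Week 12.

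The cost is one sentence, one footnote and about two additional home kits per affected woman, with results telephoned to the site, in the countries concerned only. Other countries and the visit schedule itself are unchanged.
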